6.3.2.4. Motor Function Measurement (MFM 32)

Definition

Motor Function Measurement (MFM 32) scores will be expressed as a percentage in relation to the maximum score. The score for each domain will correspond to the sum of the scores obtained by the patient for the items in that domain divided by the maximum score for the domain and multiplied by 100. The total score will be the sum of all the scores (in all the domains) divided by 96 and multiplied by 100.

MFM 32 scores include:

- Standing and transfers (D1): items 6, 8, 11, 12, 24-32
- Axial and proximal motor function (D2): items 1-3, 5, 7, 9, 10, 13-16,
 23

Sponsor: ITALFARMACO
Protocol: DSC/15/2357/53

Distal motor function (D3): items 4, 17-22

Total score (Total mark)

Analysis methodology

The absolute value of each score and change versus baseline, at each time point, will be summarized as a continuous variable using descriptive statistics.

To make best use of repeated intra-subject evaluations of MFM, the absolute change from baseline to visits 8, 9 10 and 11 (months 3, 6, 9 and 12) will be computed. These data will be analyzed using mixed model repeated measures (MMRM) analysis. Fixed effect class terms will be included for treatment, visit, visit x treatment interaction and concomitant steroid use at baseline; baseline value will be included as a covariate. An unstructured covariance matrix will be used to model the within-subject error. LSmeans and SEs and also the difference in LSmeans between treatments will be extracted by visit; SEs, 2-sided 95% CIs and 2-sided p-values will also be extracted for the difference in LSmeans. The principal focus of inference will be the results at visit 11 (month 12).

Possible need for log transformation of this variable will be assessed by check of ANCOVA model residuals. If considered non-Normal, a supportive analysis will be performed on the log scale.

The analysis will be done separately for each score.

Moreover, original values collected in eCRF as well as derived values calculated for the analysis will be listed by patient.

Data handling rules

As the MMRM approach implicitly imputes missing data as missing at random, there will be no separate analysis imputing missing values, the analysis will be based on the observed data at visits 8, 9 10 and 11.

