The absolute change in functional parameters after 12 months of therapy, as assessed by Timed Function Tests (TFTs), will be analyzed using an ANCOVA model similar to the one described for the primary endpoint. Possible need for log transformation of these variables will be assessed by check of ANCOVA model residuals.

Change in 6MWT score after 12 months of therapy

The absolute change in 6MWT score after 12 months of therapy will be analyzed using an ANCOVA model similar to the one described for the primary endpoint. Possible need for log transformation of this variable will be assessed by check of ANCOVA model residuals.

 Proportion of patients with <10% worsening in 6MWT score after 12 months of therapy

Worsening is defined as a reduction in 6MWT score after 12 months of therapy compared to baseline score. The average of the scores at screening and randomization will be used as baseline score. The proportion of patients with <10% worsening in 6MWT after 12 months of therapy will be compared between arms using a stratified Cochran Mantel-Haenszel (CMH) chi square test with a two-sided α=0.05 level. As for the primary endpoint, the stratification factor is concomitant steroid use at baseline. The proportion, along with its exact two-sided 95% CI, will be computed within each treatment group. A two-sided 95% CI for difference of proportion between the treatment groups will also be computed. In case of

17 June 2020 Page 89 of 110

patients with no 6MWT assessment at 12 months/EOS, the last available score will be used for the analysis.

Proportion of patients who lose ability to rise from floor during the study

The proportion of patients who lose ability to rise from floor during the study, as assessed by TFT, will be compared between arms using a stratified Cochran Mantel-Haenszel (CMH) chi square test with a two-sided α=0.05 level. As for the primary endpoint, the stratification factor is concomitant steroid use at baseline. The proportion, along with its exact two-sided 95% CI, will be computed within each treatment group. A two-sided 95% CI for difference of proportion between the treatment groups will also be computed. In case of patients with no 6MWT assessment at 12 months/EOS, the last available score will be used for the analysis

Proportion of patients who lose ambulation during the study

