1.1. Changes from The Study Protocol

The following changes have been made to the statistical methodology planned in the study protocol:

- Total fibrosis (primary endpoint): the main analysis will be based on log-trasformed data.
 Sensitivity analyses will be performed on the original scale and also applying different multiple imputation approaches (both MAR and MNAR)
- MRI (key secondary endpoint): same analysis planned for the primary endpoint
- Other secondary endpoints: statistical analyses will be performed by means of Mixed Model for Repeated Measures instead of ANCOVA
- Total WB dystrophin 1 and Total WB dystrophin 2 will be analyzed
- Difference between biopsy sites at baseline will be evaluated for Total fibrosis, Total CSA and MFA%

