6.3.2.5. Time function test (TFT)

Definition

Time Function Tests (TFT) evaluation will include:

- Time to climb four standard steps (4-Stair Climb)
- Time to rise from floor
- Time to walk/run 10m

Analysis methodology

The absolute value of time to 4-Stair Climb and change versus baseline, at each time point, will be summarized as a continuous variable using descriptive statistics. A box-

Sponsor: ITALFARMACO
Protocol: DSC/15/2357/53

plot of the average time to 4-Stair Climb at each visit will also be produced by treatment group.

To make best use of repeated intra-subject evaluations of 4-Stair Climb, the absolute change in time to 4-Stair Climb from baseline to visits 8, 9 10 and 11 (months 3, 6, 9 and 12) will analyzed as described for MFM using an MMRM analysis. Fixed effect class terms will be included for treatment, visit, visit x treatment interaction and concomitant steroid use at baseline; baseline value will be included as a covariate. An unstructured covariance matrix will be used to model the within-subject error. LSmeans and SEs and also the difference in LSmeans between treatments will be extracted by visit; SEs, 2-sided 95% CIs and 2-sided p-values will also be extracted for the difference in LSmeans. The principal focus of inference will be the results at visit 11 (month 12).

Possible need for log transformation of this variable will be assessed by check of ANCOVA model residuals. If considered non-Normal, a supportive analysis will be performed on the log scale.

The same analyses will be done for time to rise from floor and time to walk/run 10 m. A box-plot of the average time to rise from floor and time to walk/run 10 m at each visit will also be produced by treatment group.

Number of patients who declined to perform the test or didn't complete it (e.g. for Rise From Floor and 10-Metre Walk/Run Test) will also be provided.

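### The MMRM for the functional endpoints fits one baseline slope to all four visits, which can cost precision at month 12; a baseline × visit term removes the loss almost free

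*SAP*

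**What the plan says.** SAP 6.3.2.4 states for MFM that "the absolute change from baseline to visits 8, 9 10 and 11 (months 3, 6, 9 and 12) will be computed". The changes enter one repeated-measures model: "An unstructured covariance matrix will be used to model the within-subject error". The list of fixed effects ends with "visit x treatment interaction and concomitant steroid use at baseline; baseline value will be included as a covariate".

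SAP 6.3.2.5 gives the timed tests the same model: "Fixed effect class terms will be included for treatment, visit, visit x treatment interaction and concomitant steroid use at baseline", again with baseline as one covariate. Sections 6.3.2.6 (6MWT), 6.3.2.7 (myometry) and 6.3.3 (velocities) repeat it. Each names Visit 11 as the main focus of inference. No baseline × visit term appears anywhere.

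Protocol 13.6.2 planned something simpler. The 12-month change in MFM, timed tests, 6MWT and strength "will be analyzed using an ANCOVA model similar to the one described for the primary endpoint". SAP 1.1 declares the switch for the other secondary endpoints: "statistical analyses will be performed by means of Mixed Model for Repeated Measures instead of ANCOVA". The reason given in 6.3.2.4, 6.3.2.5, 6.3.2.6 and 6.3.3 is to exploit the repeated measurements.

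**The concern.** The treatment effect may differ by visit, but the baseline slope may not. The protocol's ANCOVA used only the 12-month change, so its slope was the month-12 slope by construction. In a progressive disease, change may depend little on baseline after three months and more after twelve. A common slope is then set mainly by the early, less variable visits and under-adjusts at month 12. What is left adds to the variance of the month-12 contrast through chance baseline imbalance, which is not negligible with 34 against 17 patients. A model adopted to make better use of the data could then be less precise at month 12 than the analysis it replaced.

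**Working it through.** **The plan's own figure.** The only sample-size calculation (Protocol 13.1, SAP 3.5) is for total fibrosis: difference 9, SD 10, 2:1, two-sided 5%. The noncentral t gives 82.1% power at 32 + 16 and 79.4% at 30 + 15, so 48 is the first 2:1 total to reach 80%. It reproduces. Nothing comparable is given for the functional endpoints, so every slope, SD, correlation and dropout rate below is an assumption.

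**Formula (complete data, large sample).** Let b be the vector of true baseline slopes at the four visits, R the residual covariance given baseline, and V the baseline variance. With treatment × visit fitted in full, the month-12 estimate is the difference in mean change minus b_c × (baseline imbalance), where the common slope is

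b_c = (1′R⁻¹b) / (1′R⁻¹1).

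The variance ratio to month-12 ANCOVA is

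1 + (b₁₂ − b_c)² V / R₄₄.

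**Timed-test example.** Assume baseline SD 5 s (V = 25), residual SD rising evenly from 1 to 2 s (R₄₄ = 4), between-visit correlation 0.6, and 34 + 17 patients. The weights in b_c are 0.90, 0.24, −0.02 and −0.13, so month 3 dominates. The ANCOVA SE is 2 × √(1/34 + 1/17) = 2 × 0.297 = 0.594.

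| Slopes, month 3 to 12 | b_c | Variance ratio | SE ratio |
|---|---|---|---|
| 0.05 constant | 0.050 | 1.00 | 1.00 |
| 0.025 to 0.10 | 0.021 | 1.04 | 1.02 |
| 0.05 to 0.20 | 0.041 | 1 + 0.159² × 25/4 = 1.16 | 1.08 |
| 0.05 to 0.35 | 0.033 | 1 + 0.317² × 25/4 = 1.63 | 1.28 |

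Simulation agrees. For 0.05 to 0.20 (2,500 trials) the SEs were 0.63 as written, 0.59 with baseline × visit and 0.59 with ANCOVA. For 0.05 to 0.35 it was 0.78 as written against 0.60, 29% larger. Shorter runs scatter around these values: 800 trials gave ratios to the corrected model of 1.09 and 1.26, and 600 trials gave 0.809 against 0.610 in the steep case. A 6MWT case (baseline SD 72 m) gave 0% for slopes 0 to 0.10 and 4% for 0 to 0.20.

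**Other structures, complete data.** With AR(1) and quarterly correlation from 0.99 down to 0.80, the formula gives SE ratios of 1.005 to 1.054. With random patient slopes correlated with baseline it gives 1.001 to 1.131. At the top of that range the variance ratio is 1.28, so 48 patients carry the information of 48/1.28 ≈ 38.

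**With dropout.** Simulation with 32 + 16 patients, random dropout by month 12, 1,000 trials per cell. The comparator is observed-case ANCOVA. The last column divides the SAP model's SE by that of the same model with baseline × visit.

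| Structure | vs ANCOVA, 0% | vs ANCOVA, 15% | vs ANCOVA, 25% | vs added term, 15% / 25% |
|---|---|---|---|---|
| Constant slope | 1.00 | 0.99 | 0.95 | 1.00 / 0.99 |
| AR(1) 0.95 | 1.02 | 0.97 | 0.98 | 1.00 / 1.02 |
| AR(1) 0.90 | 1.04 | 1.00 | 0.97 | 1.04 / 1.04 |
| Random slopes, moderate | 1.01 | 0.98 | 0.97 | 1.02 / 1.03 |
| Random slopes, strong | 1.09 | 1.11 | 1.07 | 1.14 / 1.12 |

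The corrected model was never worse than ANCOVA (0.94 to 1.00). Mean estimates under no effect were about zero in every cell.

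**Power.** For a comparison with 80% power under ANCOVA, power becomes Φ(2.80/ratio − 1.96): 78% at 1.024, 77% at 1.041, 73% at 1.09 and 70% at 1.131.

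**The case against.** Every magnitude is assumed. Protocol 4.1 says only that progression in BMD is slower and more variable than in DMD; it does not say that dependence on baseline grows over twelve months. The steep case needs baseline alone to explain 1.75²/(1.75² + 2²) = 43% of the month-12 variance. MFM and myometry were not simulated on their own scales, and MFM is a bounded percentage score.

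Complete data also hide a main advantage of the MMRM, which is that it uses partial follow-up. The protocol's handling of missing functional data is not fully defined either: its ANCOVA is modelled on a primary analysis with multiple imputation, so observed-case ANCOVA is itself an assumed comparator.

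The SAP partly covers proportional worsening. It adds a supportive log-scale analysis if residuals look non-Normal, and it analyses velocities. Finally, a common-slope MMRM is a legitimate model, and these endpoints have no stated power and no multiplicity control.

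Most of this stands and limits the size of the point. Two parts do not remove it. The log-scale and velocity analyses leave the main model unchanged, and the velocity model has the same single slope. Dropout rescues the comparison with ANCOVA, but not the comparison with the same MMRM plus one term.

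**Conclusion.** The point holds as a modest, conditional loss of precision at month 12. The loss is nil if the slope is constant and usually about 0–9% in SE if it varies. It was 9–13% against ANCOVA with complete data where progression is tightly tied to baseline and measurement error is low, and it reaches about 25–29% only with steeply rising slopes. All of these figures rest on assumed slopes, SDs and correlations.

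Three stronger readings are tempting, and the documents do not support them.

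- *The MMRM is less precise than the protocol ANCOVA.* This needs near-complete data and changing slopes. With about 15% or more random dropout the two are usually about equal unless the slopes rise steeply.
- *The month-12 estimate is biased.* The shift (b₁₂ − b_c) × imbalance averages zero over randomization and is the same quantity as the added variance, not a second harm. A deliberate stress test did produce a spurious −0.17 s (Monte Carlo SE 0.03), against −0.02 s with the term. It needed 25% dropout in the givinostat arm only, all among patients slower at baseline. Nothing in the documents indicates that pattern.
- *The trial's main result is affected.* Total fibrosis, MRS, MRI and histology have no common-slope repeated-measures model. Only secondary and exploratory endpoints are concerned.

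**What to change.** In SAP 6.3.2.4, 6.3.2.5, 6.3.2.6, 6.3.2.7 and 6.3.3, state that baseline value and baseline value × visit will be included as covariates, and make the change before unblinding. It takes one phrase per section and one model term, and needs no new data. It uses three more fixed-effect parameters. If the slope is in fact constant, the cost is at most about 1% in SE: 0.2117 against 0.2095 in the constant-slope case with 25% dropout, and nothing visible with complete data.

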6.3.2.5. Time function test (TFT)

Definition

Time Function Tests (TFT) evaluation will include:

- Time to climb four standard steps (4-Stair Climb)
- Time to rise from floor
- Time to walk/run 10m

Analysis methodology

The absolute value of time to 4-Stair Climb and change versus baseline, at each time point, will be summarized as a continuous variable using descriptive statistics. A box-

Sponsor: ITALFARMACO
Protocol: DSC/15/2357/53

plot of the average time to 4-Stair Climb at each visit will also be produced by treatment group.

To make best use of repeated intra-subject evaluations of 4-Stair Climb, the absolute change in time to 4-Stair Climb from baseline to visits 8, 9 10 and 11 (months 3, 6, 9 and 12) will analyzed as described for MFM using an MMRM analysis. Fixed effect class terms will be included for treatment, visit, visit x treatment interaction and concomitant steroid use at baseline; baseline value will be included as a covariate. An unstructured covariance matrix will be used to model the within-subject error. LSmeans and SEs and also the difference in LSmeans between treatments will be extracted by visit; SEs, 2-sided 95% CIs and 2-sided p-values will also be extracted for the difference in LSmeans. The principal focus of inference will be the results at visit 11 (month 12).

Possible need for log transformation of this variable will be assessed by check of ANCOVA model residuals. If considered non-Normal, a supportive analysis will be performed on the log scale.

The same analyses will be done for time to rise from floor and time to walk/run 10 m. A box-plot of the average time to rise from floor and time to walk/run 10 m at each visit will also be produced by treatment group.

Number of patients who declined to perform the test or didn't complete it (e.g. for Rise From Floor and 10-Metre Walk/Run Test) will also be provided.

Finally, the proportion of patients who lose the ability to rise from floor during the study (defined as patients with Rise From Floor grading = 0) will be summarized at each time point after baseline as a discrete variable using descriptive statistics. The rising from floor grading will also be summarized as discrete variable, at each time point, using descriptive statistics. The proportion of patients who lose ability to rise from floor after 12 months of therapy will be also compared between arms using a stratified Cochran Mantel-Haenszel (CMH) chi square test with a two-sided α =0.05 level. The stratification factor is concomitant steroid use at baseline. The proportion, along with its exact two-sided 95% CI, will be computed within each treatment group. A two-sided 95% CI for difference of proportion between the treatment groups will also be computed. Patients where there are missing data such that retention or loss of the ability to rise from floor cannot be determined will be included in the analysis as having lost the ability to rise from floor.

Data handling rules

In case of patients with no TFT assessments, as the MMRM approach implicitly imputes missing data as missing at random, there will be no separate analysis imputing missing values, the analysis will be based on the observed data at visits 8, 9 10 and 11.

Sponsor: ITALFARMACO
Protocol: DSC/15/2357/53

6.3.2.6. 6-Minute Walking Test (6MWT)

Definition

6 Minute Walking Test (6MWT) evaluation will include:

- Distance walked after 6 minutes
- Proportions of patients with <10% worsening in the distance walked after 6 minutes
- Proportions of patients who lose ambulation during the study

For patients who do not complete the test, the max distance walked will be considered as distance walked after 6 minutes.

For patients who were not able to do the test, due to lack of ambulation, "zero" will be imputed as maximum distance walked.

The average of the distance at screening and randomization will be used as baseline value.

Analysis methodology

The absolute value of the maximum distance walked and change versus baseline, at each time point, by treatment group will be summarized as a continuous variable using descriptive statistics. A box-plot of the average maximum distance walked at each visit will be produced by treatment group.

The absolute values of distance walked after 1, 2, 3, 4, 5, 6 minutes, number of falls and their changes versus baseline will be summarized as continues variables too. In addition, a box-plot of the mean 6MWT at each time-point will be produced for each visit by treatment group.

To make best use of repeated intra-subject evaluations of 6MWT, the absolute change from baseline to visits 8, 9 10 and 11 (months 3, 6, 9 and 12) will computed. These data will be analyzed using mixed model repeated measures (MMRM) analysis. Fixed effect class terms will be included for treatment, visit, visit x treatment interaction and concomitant steroid use at baseline; baseline value will be included as a covariate. An unstructured covariance matrix will be used to model the within-subject error. LSmeans and SEs and also the difference in LSmeans between treatments will be extracted by visit; SEs, 2-sided 95% CIs and 2-sided p-values will also be extracted for the difference in LSmeans. The principal focus of inference will be the results at visit 11 (month 12). Possible need for log transformation of this variable will be assessed by check of ANCOVA model residuals. If considered non-Normal, a supportive analysis will be performed on the log scale.

Worsening is defined as a reduction in the distance walked after 6 minutes, as assessed by 6MWT, after 12 months of therapy compared to baseline.

Sponsor: ITALFARMACO
Protocol: DSC/15/2357/53

The proportion of patients with <10% worsening, at each time point after baseline, will be summarized as a discrete variable using descriptive statistics.

The proportion of patients with <10% worsening in 6MWT after 12 months of therapy will be compared between arms using a stratified Cochran Mantel-Haenszel (CMH) chi square test with a two-sided α =0.05 level. The stratification factor is concomitant steroid use at baseline. The proportion, along with its exact two-sided 95% CI, will be computed within each treatment group. A two-sided 95% CI for difference of proportion between the treatment groups will also be computed. Patients where there are missing data such that <10% worsening in 6MWT after 12 months cannot be determined will be included in the analysis as having worsened.

The proportion of patients who lose ambulation during the study (6MWT not done because patient unable to physically perform the test), at each time point after baseline, will be summarized as a discrete variable using descriptive statistics.

The proportion of patients who lose ambulation after 12 months of therapy (6MWT not done because patient unable to physically perform the test) will be also compared between arms using a stratified Cochran Mantel-Haenszel (CMH) chi square test with a two-sided α =0.05 level. The stratification factor is concomitant steroid use at baseline. The proportion, along with its exact two-sided 95% CI, will be computed within each treatment group. A two-sided 95% CI for difference of proportion between the treatment groups will also be computed. Patients where there are missing data such that loss of ambulation cannot be determined will be included in the analysis as having lost ambulation.

The number of patients who did not attempt the test and the reasons (i.e. unable to physically perform the test, decline to perform the test or other) will be provided.

The number and proportion of patients who falls will be summarized at each time point: the mean number of falls during 6 MWT will be also summarized at each time point after baseline as continuous variable using descriptive statistics.

Data handling rules

For the MMRM analysis of 6MWT values, since the MMRM approach implicitly imputes missing data as missing at random, there will be no separate analysis imputing missing values, the analysis will be based on the observed data at visits 8, 9 10 and 11.

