### 7.1 Inclusion Criteria

Patients must meet all of the following criteria in order to be included in the study:

- Ambulant male patients aged ≥18 years to ≤ 65 years at randomization with BMD diagnosis confirmed by genetic testing.
- Able and willing to give informed consent in writing.

17 June 2020 Page 44 of 110

- Able to perform 6MWT at screening with a minimum distance of 200 m and maximum distance of 450 m.
- 4. If in treatment with systemic corticosteroids and/or ACE inhibitor, and/or  $\beta$  or  $\alpha$  adrenergic receptor blocker, no significant change in dosage or dosing regimen (excluding changes related to body weight change) for a minimum of 6 months immediately prior to start of study treatment.
- 5. Patients must be willing to use adequate contraception. Contraceptive methods must be used from Randomization through 3 months after the last dose of study treatment, and include the following:
  - True abstinence (absence of any sexual intercourse), when in line with the
    preferred and usual lifestyle of the patient. Periodic abstinence (e.g. calendar
    ovulation, symptothermal, post ovulation methods) and withdrawal are not
    acceptable methods of contraception.
  - Condom with spermicide and the female partner must use an acceptable method
    of contraception, such as an oral, transdermal, injectable or implanted steroidbased contraceptive, or a diaphragm or a barrier method of contraception in
    conjunction with spermicidal jelly such as for example cervical cap with
    spermicide jelly.

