	 3- Total Cross-Sectional Area (CSAI and CSAII) 4- Total number of fibers counted in slide III 5- Fiber size variability - Dystrophin 1- Total WB Dystrophin 1 and Total WB Dystrophin 2 	
To establish the efficacy of givinostat versus placebo administered chronically over 12 months in slowing disease progression.	Motor Function Measurement (MFM): 1- Standing and transfers (D1) 2- Axial and proximal motor function (D2) 3- Distal motor function (D3) 4- Total score (Total mark)	Mean change in MFM before and after 12 months of treatment with givinostat versus placebo.
	Time Function Tests (TFT): 1- 4-Stair ascent duration 2- Rising from floor duration 3- 10-Metre Walk/Run test duration	Mean change in Time Function Tests (time to climb four standard steps, time to rise from floor and time to walk/run 10 m) before and after 12 months of treatment with givinostat versus placebo.
	Functional Tests:	
	1- Distance walked after 6 minutes (6MWT)	Mean change in 6MWT distance before and after 12 months of treatment with givinostat versus placebo.
	2- Patients with < 10% worsening in 6MWT	Number and proportion of patients with < 10% worsening in 6MWT at the end of study will be compared between treatment groups.

OBJECTIVES	VARIABLES	ENDPOINTS
	3- Patients who lose ambulation during the study (6MWT not done because patient unable to physically perform the test)	Number and proportion of patients who lose ambulation during the study will be compared between treatment groups.
	4- Patients who lose the ability to rise from floor (Rise From Floor grading = 0)	Number and proportion of patients who lose the ability to rise from floor (from baseline through end of study) will be compared between treatment groups.
	Muscle strength measured by Hand Held Myometry (HHM):	Mean change in muscle strength (right/left knee
	 Left knee extension measurements Right knee extension measurements Left elbow flexion measurements Right elbow flexion measurements 	extension and right/left elbow flexion) before and after 12 months of treatment with givinostat versus placebo.

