6.3. Efficacy Evaluation

The efficacy analyses will be performed on patients valid for the ITT population and will be presented by planned treatment group. The primary efficacy endpoint will be also analyzed on the PP population for supportive purpose.

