6.3.3. Exploratory efficacy analysis

Evaluation of LTBP4 and osteopontin genotype

In order to determine whether the effects of givinostat versus placebo are related to the type of Mutation Exon or the LTBP4 and Osteopontin (i.e. SPP1) genotypes, three further subgroups of subjects will be defined: Mutation Exon (Exon 45, Prior to exon 45, Post-exon 45), LTBP4 (IAMM, VTTT, Other, VTTT+Other) and SPP1 (TT, GT, GG, GG+GT).

The number and proportion of patients in each subgroup will be summarized as appropriate. Further analyses are described in Section 6.5.

Evaluation of the functional test velocity

Velocity for each functional test will be computed at each visit from the following variables:

- 4-Stair ascent duration
- Rising from floor duration
- 10-Metre Walk/Run test duration

For patients with missing data TFT data due to lack of ability to perform the test, their velocity will be set equal to zero.

Velocity to 4-Stair Climb will be calculated according to the following formulas:

$$Velocity_{4-Stair\ Climb} = \frac{4}{time\ to\ climb\ 4\ stair}$$

Sponsor: ITALFARMACO
Protocol: DSC/15/2357/53

The velocity will be set to zero for patients who don't attempt the test with reason "Unable to physically perform the test" or for patients with the lowest grade (1) for the 4 Stair Climb test.

The absolute value of velocity to 4-Stair Climb and change versus baseline, at each time point, will be summarized as continuous variables using descriptive statistics.

To make best use of repeated intra-subject evaluations of 4-Stair Climb velocity, the absolute change from baseline to visits 8, 9 10 and 11 (months 3, 6, 9 and 12) will be analyzed using mixed model repeated measures (MMRM) analysis. Fixed effect class terms will be included for treatment, visit, visit x treatment interaction and concomitant steroid use at baseline; baseline value will be included as a covariate. An unstructured covariance matrix will be used to model the within-subject error. LSmeans and SEs and also the difference in LSmeans between treatments will be extracted by visit; SEs, 2-sided 95% CIs and 2-sided p-values will also be extracted for the difference in LSmeans. The principal focus of inference will be the results at visit 11 (month 12).

Velocity to walk/run 10 m will be calculated according to the following formula:

$$Velocity_{walk/run \ 10 \ m} = \frac{10}{time \ to \ walk/run \ 10 \ m}$$

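### Loss of the ability to rise from the floor is defined without a baseline condition, so a patient already at grade 0 at entry would count as an on-study loss if the definition is applied as written

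*SAP*

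**What the plan says.** The endpoint is meant as a change in status. SAP section 2 describes it as "Number and proportion of patients who lose the ability to rise from floor (from baseline through end of study"), and Protocol section 13.6.2 says "The proportion of patients who lose ability to rise from floor during the study, as assessed by TFT, will be compared between arms".

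The operational rule is narrower. SAP section 6.3.2.5 gives it as "defined as patients with Rise From Floor grading = 0", and the variable column of the SAP section 2 table reads "Patients who lose the ability to rise from floor (Rise From Floor grading = 0"). Neither mentions the baseline grade. The 12-month proportion goes into a CMH test stratified by baseline steroid use, and patients whose status cannot be determined "will be included in the analysis as having lost the ability to rise from floor".

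The denominator is the general one in SAP section 6.3: "The efficacy analyses will be performed on patients valid for the ITT population". The functional entry criterion in Protocol section 7.1, beyond being ambulant, is "Able to perform 6MWT at screening with a minimum distance of 200 m and maximum distance of 450 m". Rising from the floor is not an entry requirement.

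**The concern.** A patient who cannot rise from the floor at baseline cannot lose that ability, yet would meet the written criterion at every later visit at which he is graded 0. Such a patient can be enrolled, and no section of either document removes him from the numerator or denominator.

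The SAP does foresee inability on the timed tests. In section 6.3.3 it says "For patients with missing data TFT data due to lack of ability to perform the test, their velocity will be set equal to zero". It gives no rule for inability already present at baseline in the binary endpoint.

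The other two binary endpoints are protected. Loss of ambulation is covered by the 200 m entry minimum, and worsening on the 6MWT is defined relative to baseline in SAP section 6.3.2.6. Rise from floor has neither protection. At stake are a diluted treatment difference, lost precision, and a proportion labelled as loss that partly describes disability present at entry.

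**Working it through.** The documents give no expected rate, power or sample size for this endpoint, so there is no plan figure to reproduce. The check is textual, followed by an illustration of size.

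**Text.** Event: grade 0, or undeterminable status. Baseline condition: none stated. Denominator: ITT. Entry: ambulant, 6MWT 200–450 m. Baseline data: the timed tests are done at Visit 1 (Protocol Table 5 and section 9.1.1), so the grade needed for a baseline condition is planned to be collected.

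**Inputs for the illustration.** Planned arms of 34 givinostat and 17 placebo (SAP section 3.5), all assumed to be in the ITT set with no missing status. Assumptions not in the documents: a share *b* unable at baseline, equal in both arms and still at grade 0 at 12 months; and true new loss among able patients of 5% on givinostat and 15% on placebo.

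**Formulas.** Proportion reported under the written rule: *b* + (1 − *b*) × true loss. For example, at *b* = 20%: 0.20 + 0.80 × 0.05 = 0.24 and 0.20 + 0.80 × 0.15 = 0.32.

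Standard error of the difference under the written rule: √[pG(1 − pG)/34 + pP(1 − pP)/17].

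If only able patients are analysed, the proportions stay at 5% and 15% and the arm sizes become 34(1 − *b*) and 17(1 − *b*).

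| Unable at baseline | Written rule, givinostat vs placebo | Difference (SE), points | Difference/SE | Able patients only: difference (SE), points | Difference/SE |
|---|---|---|---|---|---|
| 0% | 5% vs 15% | 10 (9.4) | 1.06 | 10 (9.4) | 1.06 |
| 10% | 14.5% vs 23.5% | 9 (11.9) | 0.75 | 10 (9.9) | 1.01 |
| 20% | 24% vs 32% | 8 (13.5) | 0.59 | 10 (10.5) | 0.95 |
| 30% | 33.5% vs 40.5% | 7 (14.4) | 0.49 | 10 (11.3) | 0.89 |

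The written rule loses twice: the difference shrinks by the factor (1 − *b*), and the binomial variance grows as both proportions move towards 50%. Restricting to able patients costs only the smaller denominator.

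**A second set of assumed rates.** Take true losses of 10% on givinostat and 25% on placebo. Approximate power is Φ[(d − 1.96·SE₀)/SE₁], with SE₀ from the pooled proportion and SE₁ from the separate proportions.

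- At *b* = 0: d = 0.15, SE₀ = √(0.15 × 0.85 × (1/34 + 1/17)) = 0.106, SE₁ = √(0.10 × 0.90/34 + 0.25 × 0.75/17) = 0.117, power about 31%.
- At *b* = 10%, 20% and 30%: about 20%, 14% and 11% under the written rule, against 29%, 26% and 24% among able patients.

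The endpoint is weakly powered in any case, and the written rule weakens it further.

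**The case against.** **The wording already implies incident loss.** Both documents speak of losing an ability during the study, and the SAP's missing-data sentence speaks of retaining or losing it. Grade 0 can be read as stating only what inability looks like, and a programmer might add the baseline condition unprompted. So it goes too far to say that the plan will miscount. But the stated definition omits the condition, and the denominator stays open even for a programmer who notices. At 20% unable and true losses of 5% against 15%, counting these patients as events gives 24% against 32%; as non-events, 4% against 12% (0.80 × 0.05 and 0.80 × 0.15); excluding them, 5% against 15%. The SAP should make that choice.

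**The affected group may be empty.** This stands. Neither document reports anyone unable to rise at baseline. The grading scale is not defined either. That grade 0 means unable is inferred from its use here, and the lowest 4-Stair Climb grade in SAP section 6.3.3 is 1.

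**Chance imbalance.** A reader might infer that baseline imbalance could create a false treatment effect. For example, 5/17 against 4/34 unable at baseline would be reported as 29.4% against 11.8% lost with no new loss at all. The documents do not support a charge of bias or inflated type I error. Baseline inability precedes randomisation, its expected share is the same in both arms, and the CMH test and confidence interval allow for random imbalance.

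**Visibility and importance.** SAP section 6.3.2.5 summarises the grading at each time point, so grade 0 at baseline should be visible. That helps a reader but does not correct the test. The endpoint is one of many secondary endpoints, and the fibrosis conclusion is unaffected.

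**Conclusion.** The point holds as a defect in a stated definition. If SAP sections 2 and 6.3.2.5 are applied as written, an ITT patient at grade 0 at baseline and at 12 months enters the CMH test as a loss, contrary to the endpoint's description as a loss from baseline onward. Grade 0 is not the sole route to an event, because undeterminable status also counts.

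The size is unknown, since the number unable at baseline is not given and could be zero. Under equal shares unable and true losses of 5% against 15%, the reported difference falls from 10 points to 9, 8 and 7 as the share rises from 0% to 10%, 20% and 30%, with a larger standard error at each step. The harm is dilution, lost precision and a mislabelled proportion on a secondary endpoint. The type I error is not inflated.

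**What to change.** Amend both the SAP section 2 table and SAP section 6.3.2.5:

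- Restrict numerator and denominator to ITT patients with a baseline Rise From Floor grade above 0.
- Define the event as grade 0 at a post-baseline visit in those patients, taken at 12 months for the CMH test.
- Apply the rule that counts undeterminable status as lost within that set only.
- Report by arm how many patients had grade 0, or no grade, at baseline.

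The cost is a denominator smaller than the full ITT set, and a stated exception to the ITT basis for this one endpoint. From 51 patients, 10%, 20% or 30% unable would leave about 46, 41 or 36 (51 × 0.9, 0.8, 0.7). Keeping the full ITT set and counting these patients as non-events would also remove the miscount, but it shrinks the difference to the same 8 points at 20% unable and includes patients who cannot have the event.

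No new data are needed. SAP sections 3.5 and 6.6 say that baseline data were collected for all patients, so the overall number at grade 0 can be counted without unblinding. If it is zero, the amendment changes no result and simply closes the gap in wording.
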